1 BACKGROUND INFORMATION

1.1 ACAM2000®

ACAM2000 (Smallpox (Vaccinia) Vaccine, Live) is a live, attenuated vaccinia virus derived from ACAM1000, a similar smallpox vaccine produced in cell culture by plaque-purification cloning from Dryvax® (Wyeth Laboratories, Marietta, PA). Dryvax was prepared from calf lymph, which was purified, concentrated and dried by lyophilization (1). It was prepared with a seed virus derived from the New York City Board of Health (NYCBOH) strain of vaccinia.

Vaccinia vaccine is a highly effective immunizing agent that brought about the global eradication of smallpox. The last naturally occurring case of smallpox occurred in Somalia in 1977. In July 1979, the World Health Organization (WHO) certified that the world was free of naturally occurring smallpox (2).

Routine vaccinia vaccination was discontinued in 1971 (3). In 1976, the recommendation for routine vaccination of health care workers was also discontinued (4). In 1982, the only active licensed producer of vaccinia vaccine in the United States of America (USA), Wyeth-Lederle Vaccines and Pediatrics (subsidiary of American Home Products) discontinued production for general use, and in 1983, distribution to the civilian population was discontinued (5). For several years all military personnel continued to be routinely vaccinated; however, only selected groups of military personnel are currently vaccinated against smallpox (1). The Dryvax vaccine has now been replaced by ACAM2000, which is now kept by the Centers for Disease Control and Prevention (CDC) in Atlanta.

To ensure safe use of vaccinia vaccines, satisfactory stocks of vaccinia immune globulin (VIG) are necessary for managing specific vaccination complications (6). VIG is an isotonic sterile solution of the immune globulin fraction of plasma from persons vaccinated with vaccinia vaccine. The first commercially available VIG, manufactured by Baxter Healthcare, was originally approved by Center for Biologics Evaluation and Research (CBER) in 1968 but, like Dryvax, is no longer produced. Emergent BioSolutions Canada Inc. (Emergent) currently manufactures Vaccinia Immune Globulin Intravenous (VIGIV), which was approved by the Food and Drug Administration (FDA) in 2005.

1.2 Clinical Study Rationale

There is increased interest in building up the national stockpile of vaccinia vaccine as protection against the deliberate release of smallpox (variola virus), and VIGIV is necessary to treat potential serious vaccination-related complications. To produce VIGIV, a source of high titer anti-vaccinia plasma is required. However, plasma donors require booster vaccination to produce anti-vaccinia antibody titers required for successful production of VIGIV.

In previous plasma collection program study (VA-001) the Dryvax vaccine was used to elevate anti-vaccinia immune globulin titers in subjects and then plasma was collected to produce VIGIV. In a follow up study (VA-006), subjects were vaccinated using the ACAM2000 smallpox vaccine, and their plasma was collected to compare the VIGIV manufactured from plasma collected from donors

vaccinated with ACAM2000 to VIGIV manufactured from plasma previously collected from donors vaccinated with the Dryvax smallpox vaccine. ACAM2000 vaccinated donors produced plasma titres that were sufficient for pooling to manufacture VIGIV. In general, the key quality attributes of the ACAM2000 product fell within the range of results seen for VIGIV manufactured from Dryvax vaccinated donors.

In this study (VA-008), healthy adult male and female volunteers who meet the requirements for source plasma donors and study entry criteria will be vaccinated with the ACAM2000 smallpox vaccine for collection of plasma to be used in the manufacture of VIGIV. There are possible risks associated with ACAM2000 vaccination. To ensure the safety of plasma donors, risk factor screening procedures and the collection of post-vaccination safety data will be assessed throughout the study.

To reduce these possible risks the safety of each donor will be assessed throughout the study and the following safety measures will be taken:

- Training of the study staff on the possible related adverse events following ACAM2000 vaccination.
- Training of the study staff on vaccination site inspection (appearance and evaluation) at each study visit.
- Training of all investigators involved in the vaccination of subjects on administration of the ACAM2000 vaccine.
- Education of the study subjects on the possible risks involved with ACAM2000 vaccination and providing them with *ACAM2000 Medication Guide*.
- Thorough screening process to exclude subjects with higher risk of experiencing serious complications following vaccination e.g., excluding subjects with immunodeficiency, cardiovascular disease or heart condition, etc. (for a complete list see exclusion criteria section [4.2](#)).
- Vaccination of subjects who were previously vaccinated with a smallpox vaccine (Dryvax or ACAM2000) and who do not have any unresolved adverse events from previous smallpox vaccination.
- Exclusion of subjects who are pregnant or are planning to become pregnant and performing pregnancy tests at each study visit for women of childbearing potential.
- Safety evaluation at each study visit by assessments of pericarditis/myocarditis symptoms, adverse events and subject reminders for vaccination site care.
- An algorithm ([Appendix II](#)) for suspected pericarditis/myocarditis will be followed to ensure subject safety and follow-up. If a subject who needs to have an EKG performed at BPL is not able to complete an in-person study visit due to COVID-19 restrictions, he/she will be instructed to go to the nearest emergency room (ER). The subject will be required to bring back the medical records to the next protocol scheduled visit. If a subject is not able to obtain the records or attend

the visit in person then the copy of the medical records is to be requested from the ER and sent to the Principal Investigator.

- A final safety assessment at Day 90 post-vaccination. All related adverse events (AEs) (serious and non-serious) will be followed to resolution or stabilization as applicable (may extend beyond Day 90 post-vaccination).
- Safety of subjects will be monitored throughout their study participation utilizing a combination of centralized and onsite monitoring (risk-based monitoring approach). Sites will be monitored and data will be reviewed on a monthly basis according to a Medical Monitoring Plan. A Data and Safety Monitoring Board (DSMB) will be established to meet at pre-defined intervals and have ad hoc meetings (if necessary) to review study data and independently ensure the safety of subjects participating in this study according to the DSMB charter.

1.3 Plasmapheresis

Blood is composed of plasma, blood cells, and platelets. Plasma is the clear, yellowish fluid portion of blood, lymph, or intramuscular fluid in which cells are suspended. It makes up about 55% of total blood volume. It is composed of mostly water and contains dissolved proteins, glucose, clotting factors, mineral ions, hormones and carbon dioxide.

Plasma will be collected by an automated plasmapheresis method, which involves a process whereby a needle is placed in the donor's arm, the device collects whole blood, separates the blood components by centrifugation, retaining the plasma portion of the blood and returning the remaining blood components to the donor through the same needle.

Plasmapheresis procedures will be conducted at FDA approved plasma collection sites, and will be conducted according to the site's FDA-approved standard operating procedures (SOPs) for plasma collection. The frequency of plasma donation and volume of plasma collected at each donation will vary by weight and will be conducted in accordance with the United States Code of Federal Regulations (CFR) Title 21 part 640.65.

Study subjects that have been vaccinated with ACAM2000 may not undergo plasmapheresis until at least 10 days after vaccination.

Donors who have been vaccinated with ACAM2000 under this protocol, who do not exhibit vaccine complications, should be deferred from participation in any blood donor program except for the specific collection of anti-vaccinia antibody until after the vaccination scab has separated spontaneously, or for 30 days post-vaccination, whichever is the later date. If scab is removed prior to spontaneous separation, FDA recommends that the donor be deferred for two months after vaccination.

For donors who have been vaccinated with ACAM2000 under this protocol, who have experienced complications of vaccination, FDA recommends that these donors be deferred from participation in

any other blood donor program until 14 days after all vaccine complications have completely resolved.

Sites must follow their FDA approved procedures for donor eligibility and deferral in addition to the eligibility requirements outlined in section 4.

2 STUDY OBJECTIVES AND PURPOSE

2.1 Hypothesis

The protocol will allow for the safe use of ACAM2000 in a plasma donor vaccination program.

2.2 Primary Objective

This protocol is being conducted to vaccinate plasma donors with the ACAM2000 smallpox vaccine thereby inducing an immune response resulting in high anti-vaccinia antibody titers. The collection of donor plasma will be used in the manufacturing of Vaccinia Immune Globulin Intravenous (VIGIV). The objective of this protocol is to ensure the safety of plasma donors vaccinated with ACAM2000 through the implementation of risk factor screening procedures and the collection of post-vaccination safety data.

3 STUDY DESIGN

Open label, single arm, multi-center, vaccination program of plasma donors. Donor safety will be evaluated following administration of the ACAM2000 vaccine.

3.1 Anticipated Centers

Multiple FDA licensed plasma collection centers will be involved in this study.

3.2 Sample Size

Ongoing enrollment to fulfill VIGIV manufacturing requirements for current contracts.

3.3 Randomization and Blinding

There is no randomization or blinding in this study.

3.4 Criteria for Stopping or Terminating the Study

Emergent and the Principal Investigator may elect to terminate the study early as defined by the clinical study agreement. The study may be terminated at any or all sites for any of the following reasons:

- The safety data demonstrate or strongly suggest that the study treatment (or participation in the study) is unsafe. The Principal Investigator and sponsor, with input from the DSMB, will be responsible for ongoing review of safety data. The Principal Investigator will initially assess seriousness, causality and intensity (severity) of an adverse event.
- The protocol or conduct of the study is flawed such that the safety or rights of the study subjects may be adversely affected.
- The ethics committee has withdrawn the approval for the study and has denied reconsideration.
- Sponsor agrees with DSMB recommendation for stopping, terminating or suspending the study based on DSMB Charter.
- Poor recruitment.
- Relocation of the Principal Investigator or reallocation of Principal Investigator's responsibilities, or disqualification of the Principal Investigator by order of the regulatory authority.
- Non-adherence to the protocol or unavailability of the Principal Investigator or his/her staff for the sponsor's (or their authorized representative) monitoring personnel.
- Inadequate evidence of the Principal Investigator's personal conduct or supervision of the study.
- Change of research strategy or change of management priorities.
- Imposition of clinical hold by a regulatory authority.

Any decision to voluntarily suspend or terminate a clinical study will be carefully reviewed and fully justified. The sponsor will notify the FDA and the Central Institutional Review Board (IRB) of any suspension or termination, along with justification for restarting or terminating the study as applicable.

The Principal Investigator must notify the IRB in writing of the study's completion or early termination. Emergent must receive a copy of the notification letter from the IRB indicating receipt of the completion or early termination letter.

4 SELECTION AND WITHDRAWAL OF SUBJECTS

4.1 Subject Inclusion Criteria

Subjects must meet the inclusion criteria to participate in the study.

- Signed written informed consent.
- Age 18 to 65
- Normal and healthy (immune competent) as determined by medical history, physical exam, vital signs and clinical laboratory tests during the screening period

- If the lab result for quantitative immunoglobulin A (IgA) is lower than 15% below normal range, the subject may not proceed further in the screening process.
- Subject must meet all required subject suitability criteria that pertain to normal source plasma donors as per 21 CFR 640.63.
- Negative human immunodeficiency virus (HIV) serology during screening period.
- Subject must have been previously immunized for smallpox, at ≥ 3 years prior to commencement of screening assessments, and vaccination history must be confirmed by oral or written history and the presence of a visible pathognomonic smallpox vaccination scar.
- Female subjects of childbearing potential must agree to use highly effective birth control methods. Acceptable methods of birth control include: IUD (inserted at least seven days prior to vaccination), hormonal implant (inserted at least 30 days prior to vaccination), oral contraceptive regimen (started at least 30 days prior to vaccination) and injectable hormone (injected at least 30 days prior to vaccination). The decision to allow use of hormonal contraceptives should be based on the potential for interactions with concomitant medications. Birth control method must be used throughout the study until scab separates. Females of non-childbearing potential are defined as being surgically sterile or meeting postmenopausal requirements and all women must be educated on risks of vaccine to an unborn child. Postmenopausal is defined as either >12 consecutive months with no menses without an alternative medical cause or $FSH \geq 40$ mIU/mL or if these criteria are not met and the woman is >50 years, she may participate if she agrees to undergo pregnancy testing requirements and agrees to use an effective birth control method such as barrier contraception for four weeks post-vaccination or until the scab separates, whichever is longer. Written confirmation is required for surgical sterility and birth control methods. As a COVID-19 precautionary measure, women of childbearing potential will not be included in the study temporarily.

4.2 Subject Exclusion Criteria

Subjects who have any of the exclusion criteria at screening and/or baseline will be excluded from participation in this study.

- History of severe related adverse event(s) from previous participation in VA-001 or VA-006 trials or to any smallpox vaccination.
- The subject, or a household contact or other close/intimate contact of the subject has ANY of the following:
 - Eczema, history of eczema, exfoliative skin conditions, wounds, burns, or other skin conditions at the investigator's discretion.
 - A history of immunodeficiency.

- Currently or has recently received radiotherapy or chemotherapy, adrenocorticotropic hormone (ACTH), corticosteroids, or immunosuppressive drugs. This includes any route of administration (including topical) for any duration of time at any dose for at least one month prior to vaccination.
 - Eye disease treated with topical steroids.
- Known or suspected disorders of immunoglobulin synthesis.
- Leukemia, lymphomas of any type, melanoma, or other malignant neoplasms affecting the bone marrow or lymphatic systems.
- Has been diagnosed with cancer and who will be undergoing chemotherapy or radiation therapy during the vaccination healing time.
- Is a transplant recipient (except for corneal transplant).
- Is pregnant, planning pregnancy or breastfeeding (female subjects must have negative urine pregnancy test prior to vaccination).
- Household or other close/intimate contact(s) under the age of 12 months.
- History of allergies to phenol, any of the antibiotics listed in the vaccine content, or any other component of ACAM2000 or its diluents (see section [5.1](#)).
- Subjects with kidney disease (except kidney stones).
- Subjects with abnormal EKG at screening (if applicable).
 - To mitigate the risk of enrolling subjects at higher risk of developing cardiac adverse events and potentially jeopardizing subject safety an EKG will be performed prior to vaccination with ACAM2000 smallpox vaccine in all potential subjects ≥ 50 years old and for all potential subjects < 50 years old with two cardiovascular disease risk factors as listed immediately below including severely or morbidly obese or higher obesity classification ($BMI \geq 36$), high blood pressure, high blood cholesterol, diabetes or high blood sugar, a first degree relative who had a heart condition before the age of 50 and current tobacco smokers. EKG results will be reviewed by a qualified third party board-certified cardiologist and will be reported to the site.
 - All subjects with EKG interpreted as 'Abnormal, Significant' by the third party cardiologist will be excluded. Inclusion of subjects with 'Abnormal, Insignificant' EKG will be based on the Principal Investigator's discretion.
- Subject has three (or more) of the following cardiovascular disease risk factors:
 - Severely or morbidly obese or higher obesity classification ($BMI \geq 36$)
 - High blood pressure diagnosed by a doctor
 - High blood cholesterol diagnosed by a doctor

- Diabetes or high blood sugar diagnosed by a doctor
- A first degree relative (for example, mother, father, brother, sister) who had a heart condition before the age of 50
- Currently smokes tobacco (cigarettes)
- Cardiovascular disease or heart condition diagnosed by a doctor at any time in the past, with or without symptoms, including:
 - Arrhythmia
 - Syncope related to cardiac disease
 - Previous myocardial infarction
 - Angina
 - Coronary artery disease
 - Congestive heart failure
 - Cardiomyopathy
 - Stroke or transient ischemic attack
 - Myocarditis
 - Pericarditis
- Chest pain or shortness of breath with activity (such as climbing stairs), peripheral edema, heart palpitations, dry cough, irregular heartbeat, excessive fatigue, unexplained syncope
 - Subjects will be solicited for symptoms suggestive of cardiovascular problems (as stated above) at screening and prior to vaccination. If subject has any of these symptoms, they will not be included in the study or if already included, they will not be vaccinated unless follow-up results confirm that the symptoms were isolated and not related to cardiovascular problems.
- Other heart conditions being treated by a physician

4.3 Subject Withdrawal

The subjects must be available, without coercion, for all parts of the study.

If continued participation jeopardizes the subject's health, the subject should be withdrawn from the study. The Principal Investigator is encouraged to consult the sponsor prior to the withdrawal of any subject, except in the event of a medical emergency. The reason for withdrawal of any subject must be clearly documented on the study source documents and the appropriate electronic Case Report Form (eCRF).

4.3.1 Subject Withdrawal Criteria

All subjects are free to withdraw from participation in this study at any time, for any reason, specified or unspecified, and without penalty or loss of benefits to which the subject is otherwise entitled.

In addition, subjects may be withdrawn from the study for any of, but not limited to, the following reasons:

1. The subject develops an intercurrent illness (adverse event) that prevents study completion.
2. The sponsor elects to stop the study.
3. The subject is not compliant with the requirements of the study to the satisfaction of the investigator and/or sponsor (withdrawn by the investigator).
4. The subject elects to stop further participation in the study (consent withdrawn).
5. Subject is lost to follow up.
6. The subject does not meet the entry criteria for the study but was erroneously entered into the trial, or no longer meets entry criteria after entry into the study per protocol.
7. The opinion of the Principal Investigator that it is unwise for the subject to continue in the study.

If a subject is withdrawn from the study, they will not be re-entered into the study for any reason.

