4.3.3 Follow-up for Withdrawn Subjects

Every attempt will be made to ensure that subjects who are withdrawn, or who withdraw from the study during the active treatment or follow-up period, will complete all safety and assessments for the early withdrawal visit as outlined in this protocol. The Principal Investigator should inform the subjects that these assessments are for their own safety.

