6.9 Additional Assessments for Subjects with Symptoms of Pericarditis and/or Myocarditis

In the event that a subject presents at any assessment with symptoms or findings suggestive of pericarditis and/or myocarditis (e.g., chest pain, heart palpitations, irregular heartbeat, excessive fatigue, peripheral edema, shortness of breath, unexplained syncope, dry cough) the investigator will conduct additional assessments (e.g., physical exam including pericardial rub, assess for diminished heart sounds, pleural effusion, and peripheral edema) as required to confirm or rule out a clinical diagnosis of pericarditis/myocarditis. If unable to perform additional assessments in person, subject will be referred to the ER for further evaluation.

If isolated symptom(s) is/are mild and not likely to be pericarditis and/or myocarditis the site will follow up with the subject after 24 to 48 hours to assess if the symptom(s) persists. If resolved, the subject may continue in the study according to the scheduled visits. Subjects should be instructed to report reoccurrence, worsening of, or presentation of additional symptoms immediately to the site physician.

If the subject symptom(s) is/are indicative of pericarditis and/or myocarditis at any visit or if after 24 to 48 hours the reassessment suggests the symptom(s) is/are persisting and/or worsening, the site will perform an EKG. The EKG will be interpreted by an off-site board certified cardiologist provided by the EKG supplier. If a subject is not able to make the in-person visits due to COVID-19 related travel restrictions, then the subject exhibiting potential symptoms of pericarditis/myocarditis needing an EKG will be referred to ER.

If following off-site cardiologist EKG review the subject is not likely to have pericarditis and/or myocarditis, the site will follow-up with the subject after 24 to 48 hours to assess if the symptom(s) persists. If resolved, the subject may continue in the study according to the scheduled visits. If after off-site cardiologist EKG review pericarditis and/or myocarditis is likely, the subject should immediately be referred to a local board-certified cardiologist for further assessment and follow-up where national criteria for evaluation and treatment based upon local standards of care will be applied.

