5 MISSING VALUES

Missing data are assumed to occur at random and to be minimal, thus no imputation methods will be used.

All summary statistics will be calculated with missing values omitted from analysis. The sample size for summary statistics will be provided in all summary tables.

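### Withdrawal reason 6 can end scheduled safety follow-up of an already vaccinated donor because an entry criterion was unmet or has newly arisen

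*Protocol*

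**What the plan says.** **Withdrawal.** Protocol 4.3.1 says that "subjects may be withdrawn from the study for any of, but not limited to, the following reasons". Reason 6 covers a subject who was entered in error, and one who "no longer meets entry criteria after entry into the study per protocol". Neither part mentions whether the vaccine has been given. The section adds that a withdrawn subject cannot come back.

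**Checks after vaccination.** Sections 6.3 to 6.8 ask whether exclusion criteria have arisen. The items named are skin conditions, living conditions or close contacts, and pregnancy. In 6.7 and 6.8 the check applies only while the scab is still in place.

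**What a withdrawn subject keeps.** Section 4.3.3 promises every attempt to ensure that withdrawn subjects "will complete all safety and assessments for the early withdrawal visit as outlined in this protocol". The note in 6.6 promises efforts to follow an unhealed vaccination site and to make the Day 90 contact. Section 6.7 follows related adverse events until they resolve or stabilise. Section 7.9 follows all adverse events for at least four weeks after vaccination.

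**Analysis.** SAP section 5 states: "Missing data are assumed to occur at random and to be minimal, thus no imputation methods will be used". SAP Appendix III plans a listing of discontinued subjects (16.2.1.1). Appendix I has no table of discontinuations by reason.

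**Entry errors in practice.** The 2019 note to file attached to the SAP reports that several subjects re-enrolled at a different site without disclosing earlier participation. It says they may not have met the three-year interval.

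**The concern.** Vaccination is a single event on Day 0. Ending participation after that cannot reduce the donor's exposure. It only stops the visits at which adverse events and cardiac symptoms are solicited, and SAP 3.1 names both as safety endpoints.

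Reason 6 also selects whom it removes. Protocol 7.8 names heart disease, eczema and other exfoliative skin conditions, and pregnancy among the conditions that raise the risk of serious complications. A vaccinee found after Day 0 to have one of these is someone whose outcome the study most needs to see. If that donor leaves before any event, a later event may go undetected. The loss would then be related to risk, while the SAP treats missing data as random and small.

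**Working it through.** There is no figure in the plan to reproduce. The check is a reading of the text plus a count of assessments.

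**1. Does reason 6 reach vaccinated subjects?** Yes, as written. The part on entry in error has no time limit, and such an error can come to light after Day 0. The note to file shows that undisclosed ineligibility is a practical possibility here. It does not say when those re-enrolments were discovered or that anyone was withdrawn because of them. The part on no longer meeting criteria can be matched to the post-vaccination check for skin, contact and pregnancy items.

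**2. Which safeguards detect a new event after withdrawal?**

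| Provision | What it does | Detects a new event? |
|---|---|---|
| 4.3.3 and 6.6 | Early-withdrawal visit, including peri/myocarditis symptoms | Once |
| 6.6 note | Efforts to follow an unhealed site and to make the Day 90 contact; the wording leaves open whether the Day 90 effort covers all withdrawn subjects | Best effort |
| 6.7 | Weekly visits for related events still unresolved | Only if a related event is already known |
| 7.9 | Follows adverse events for at least four weeks | Sets no detection visits for a withdrawn subject |

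For a donor with no event, or one judged unrelated, only the first two rows give detection contacts.

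**3. How many scheduled assessments are lost?** In the Schedule of Events, post-vaccination peri/myocarditis assessments for a subject with a take fall on Days 3, 7, 12, 21, 28, 35 and 90, so there are 7. Adverse events are collected on the same days.

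Let R be the number of scheduled days after the last visit attended, and k the number of replacement contacts that take place. Net loss = R − k. Here k = 2 if the early-withdrawal visit and the Day 90 contact both happen, and k = 1 if Day 90 fails.

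| Withdrawn after | R | Net loss, k = 2 | Net loss, k = 1 |
|---|---|---|---|
| Day 3 | 6 | 6 − 2 = 4 | 6 − 1 = 5 |
| Day 7 | 5 | 5 − 2 = 3 | 5 − 1 = 4 |
| Day 12 | 4 | 4 − 2 = 2 | 4 − 1 = 3 |
| Day 21 | 3 | 3 − 2 = 1 | 3 − 1 = 2 |
| Day 28 | 2 | 2 − 2 = 0 | 2 − 1 = 1 |

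The count treats the early-withdrawal visit as a separate contact that does take place. The weekly visits in 6.7 would replace the lost assessments for a donor with an unresolved related event, so the table does not describe that donor.

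**4. Can the bias be sized?** No. The documents give no number or rate of reason 6 withdrawals.

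**The case against.** The strongest reply is that the protocol does not abandon cardiac cases, and that is correct. A reader might infer that a vaccinee who develops myocarditis, pericarditis or cardiac symptoms thereby fails an entry criterion and is dropped. The symptom criterion, "Chest pain or shortness of breath with activity (such as climbing stairs), peripheral edema, heart palpitations, dry cough, irregular heartbeat, excessive fatigue, unexplained syncope", does closely match the list solicited in 6.9. The documents do not support the inference:

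- Section 4.2 ties the criteria to entry: "Subjects who have any of the exclusion criteria at screening and/or baseline will be excluded from participation in this study".
- The diagnoses are worded as history: "Cardiovascular disease or heart condition diagnosed by a doctor at any time in the past, with or without symptoms, including". The symptom rule concerns whether a subject is included or vaccinated.
- The post-vaccination check names no cardiac item.
- In 6.9, the sentence "If resolved, the subject may continue in the study according to the scheduled visits" is set against EKG and cardiology referral, not against withdrawal. Suspected cases are then followed like unresolved related events, which means more cardiac follow-up.
- An adverse event that prompts withdrawal has already been seen. SAP section 6 counts a subject once per preferred term, so leaving afterwards does not lower that event's incidence.

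The rate of 5.7 per 1000 in Protocol 7.8 cannot be used to size the problem either. It is for primary vaccinees, and every donor here must have been vaccinated before.

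Other replies stand in part. Withdrawal is optional. Its reason is recorded in the eCRF, and discontinued subjects are listed. Reason 6 has a natural use between consent and vaccination. Reasons 1 and 7 and the open-ended list would still allow withdrawal of a vaccinee, so an edit to reason 6 alone would be incomplete. For a positive pregnancy test the visit sections call for reporting and do not mention withdrawal. None of this supplies scheduled detection for a withdrawn vaccinee who has had no event.

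**Conclusion.** The point holds in a limited form. Reason 6 permits, but does not require, an end to scheduled safety follow-up for a vaccinated donor who was entered in error or has a newly arisen skin, contact or pregnancy criterion. The harm is possible missed detection in donors with no event yet, or with one judged unrelated. For a donor with a take the net loss is 4 or 5 of 6 cardiac assessments after Day 3, and 3 or 4 of 5 after Day 7.

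The direction of any bias would be toward too few events. Its size cannot be estimated, and the documents do not show that it has occurred. The link to risk rests on the conditions that 7.8 names. It is weaker for a short interval since the last vaccination: 7.8.1 says a shorter interval makes a non-take more likely and does not call it a higher risk. With only a listing of discontinued subjects planned, risk-related loss would not show in the summary tables.

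This is a cheap improvement. It does not show that cardiac cases go unfollowed.

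**What to change.** Reconcile 4.3.1 with 4.3.3, 6.6 and 6.7:

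- For a vaccinated subject, an entry criterion found unmet or newly arisen is recorded as a deviation or an adverse event. It does not by itself end the safety assessments already scheduled through Day 90 (Day 35 for non-takes), unless consent is withdrawn.
- Reason 6, as a ground for leaving the study, then applies only before vaccination.

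Placing the first statement as a general rule for vaccinated subjects, and not only inside reason 6, also deals with the overlap with the other withdrawal reasons.

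Eligibility to donate plasma stays with the existing site procedures. The protocol already separates the two: in 6.4, non-takes may not donate yet remain in follow-up to Day 35. The clinical pathway in 6.9 needs no change for this point.

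The cost is a wording change and a few more visits or calls, all of them already in the schedule, for what should be a small number of subjects.
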